3.5 Table, Figures and Listings Conventions

Analyses of PCP participants described in this document are for the screened, randomized and study completer populations. They include the following:

- Summary of the screened PCPs by site and overall

- Summary of the randomized PCPs by site, intervention treatment arm and overall
- Summary of the study completers by intervention treatment arm and overall

Tables will include a total column or row. The descriptive text in the SAP, and the name of the table, listing, or figure, will indicate whether it is by treatment arm or site.

Analyses of patient participants include the population sets for the prescreened, screened, Intent-to-Treat, per protocol, complete case, primary outcome available, primary outcome not available, and study completer populations. They include the following:

- Summary of prescreened population by site and overall
- Summary of screened population by site and overall
- Summary of Intent-to-Treat population by intervention treatment arm, by site and overall
- Summary of per protocol population by intervention treatment arm, by site and overall
- Summary of completer case population by intervention treatment arm, by site and overall
- Summary of primary outcome available population by intervention treatment arm and overall
- Summary of primary outcome not available population by intervention treatment arm and overall
- Summary of study completer population by intervention treatment arm and overall.

Similarly, tables will include a total column or row. The descriptive text in the SAP, and the name of the table, listing, or figure, will indicate whether it is by treatment arm or site.

Continuous variables will be summarized using the following descriptive statistics: n (non-missing sample size), mean, standard deviation, percentiles (median, 25th and 75th percentiles, maximum and minimum). Categorical variables will be summarized in terms of frequencies and percentages in terms of non-missing counts.

4.0 PARTICIPANT ENROLLMENT, DISPOSITION, AND VISIT ATTENDANCE

4.1 PCP Participant

4.1.1 Participant Enrollment

The number of PCP participants screened, and the corresponding reasons for ineligibility on screening, will be summarized by site.

The distribution of individual PCP participant level and PCP cluster level treatment assignments by site will be presented.

The number of patient participants enrolled per PCP cluster will be presented by site and treatment arm both numerically and categorically.

4.1.2 Participant Disposition

PCP participants are considered early study terminations if the Provider Eligibility Review (PCP) form indicates the PCP withdrew from the study early and are defined as study completers if the withdrawal section is not complete on the form. PCP participant disposition will be summarized by site and treatment arm for the number of PCP participants completing the study, the number of PCP participants terminating early from the study, and the reasons for early study termination.

The CONSORT flow diagram will be generated for PCP participants [2].

4.2 Patient Participant

4.2.1 Participant Enrollment

The number of patient participants prescreened and screened, and the corresponding reasons for ineligibility on prescreening and screening, will be summarized by site. Note that patient participants may prescreen multiple times. Patient participants that prescreened multiple times will be considered for all attempts. The summary of prescreening will present both number of attempts and number of unique patients that prescreened eligible. Note that patient participants may be screened more than once. Patient participants who were screened more than once will only be considered for the last completed screening.

The trajectory of actual enrollments versus the expected number of enrollments (according to the date of site open for enrollment and under the assumption that eight patient participants are expected to be enrolled per month per site until November 2021 for the 5 initial sites, and 4.5 patient participants per site per month for the remaining 4 open sites until the date the proposed target of 300 is reached or the end of enrollment whichever occurs first) along with the proposed number of enrollments (300) will be graphed by site and overall. Proposed versus actual enrollments will be summarized by site in a tabular fashion.

The distribution of treatment assignments by site will be presented.

4.2.2 Participant Disposition

Patient participants are defined as study completers if the Month 12 Study Visit is completed as indicated on the Study Completion (STC) form and they are considered early study terminations if this visit is not completed. Patient participant disposition will be summarized by site and treatment arm for the number of patient participants completing the study, the number of patient participants terminating early from the study, and the reasons for early study termination.

The CONSORT flow diagram will be generated for patient participants [2].

4.2.3 Healthy Living Monthly Survey Completion

The primary outcome and several secondary outcomes are measured using the Healthy Living Monthly Survey (HLM). The self-reported HLM Survey assesses for risky opioid use and for specific classes of non-opioid substance use in the past 30 days for 12 months (12 surveys). The number of days of risky (illicit or nonmedical) opioid use is assessed in the monthly self-administered surveys that specify the number of days of illicit opioid use and of nonmedical opioid use in the past 30 days (range is 0-30 days). Also, days of non-opioid substance use are measured using the same approach as the days of opioid use for the following categories: binge drinking (4+ drinks/day for women; 5+ drink/day for men), benzodiazepines, illicit stimulants (cocaine and methamphetamine), prescription stimulants (amphetamines), marijuana, and other drugs, in the past 30 days. The number and percentage of patient participants submitting the survey and the number and percentage of patient participants completing the risky opioid use questions in each of the monthly surveys will be summarized by site and treatment arm.

4.2.4 Visit Attendance

The number and percentage of patient participants attending the five study visits will be summarized at baseline and at 3, 6, 9, and 12-months post-baseline by treatment arm. Information on missed visits during the study will be presented by treatment arm, including the number of missed visits, the number of patient participants with at least one missed visit, and the reasons for the missed visits. The expected number of study visits is calculated based on the general rule that five total visits are expected per patient participant. The average number of missed visits per patient participant will be calculated by dividing the number of missed visits by

the number of patient participants. For early study terminations, visits are only considered missed during active study participation if they occur before the study termination date.

5.0 ANALYSIS OF PARTICIPANT BASELINE CHARACTERISTICS

5.1 PCP Participant

Baseline demographics and characteristics including gender, age, ethnicity, race, and medical profession will be summarized by site and treatment arm for all randomized PCP participants. Age will be summarized as a continuous and categorial variable. A summary of baseline demographics and characteristics will also be presented for study completers by treatment arm. Because randomization is expected to produce balance at baseline between the treatment arms of the trial, comparisons of treatment arms with respect to baseline characteristics will be descriptive. If meaningful differences between treatment arms are suspected, statistical testing may be performed.

5.2 Patient Participant

Baseline demographics and characteristics including sex, age, ethnicity, race, education level, marital status, employment status, insurance status, time spent in jail or prison, number of risky opioid, binge alcohol, benzodiazepine, stimulant, marijuana, and other drug use days at prescreening, prescription for opioids in past 6 months at prescreening (y/n), COMM score, overdose risk behavior score, pain scores, anxiety, depression, sleep quality, health related quality of life, and addiction treatment and harm reduction program utilization will be summarized by site and treatment arm for all enrolled patient participants. Age will be summarized as a continuous and categorial variable. A summary of baseline demographics and characteristics will also be presented for study completers by treatment arm. Additionally, a summary of baseline demographics and characteristics by treatment arm will also be presented for the patient participants with the 6-month primary outcome available vs without the 6-month primary outcome available. It is expected that the balance of baseline characteristics at the patient participant level might not be ideal since randomization is conducted at the PCP cluster level. Comparisons of treatment arms with respect to baseline characteristics will be descriptive. If meaningful differences between treatment arms are suspected, statistical testing may be performed.

6.0 INTERVENTION EXPOSURE

6.1 STOP Exposure

The STOP intervention is comprised of several components delivered by the PCP, the nurse care manager (NCM), and the telephone health coach (THC). This information is captured on intervention checklists completed by the research staff, PCPs, the NCMs, and the THCs.

The number and percentage of patient participants in the STOP arm who received the PCP brief advice within and outside of the 10-day window, who received the Health Living Study Report Card and opioid overdose pamphlet, and who received the video doctor, and average number of minutes spent with PCP discussing opioid use will be presented by site.

The number and percentage of patient participants in the STOP arm who were educated on overdose prevention by the NCM, who received the workbook, who received information on how to access naloxone, and the distribution of contacts with the NCM over the 12 months of study participation will be presented by site. Receiving information to access naloxone is defined as any of the following: received a prescription, was given information to access it, was handed Narcan kit, or already has it, as reported on the NCM Intervention Checklist (NIC) form.

The number and percentage of patient participants in the STOP arm who completed 0, 1, 2, ..., 6 coaching sessions, and the distribution of coaching sessions completed per participant will be presented by site.

6.2 EUC Exposure

Information on the exposure of patient participants in the EUC arm (receipt of educational materials and video viewing) is not collected in the data system and will not be presented.

7.0 EFFICACY ANALYSIS

7.1 Definition of the Primary Outcome Measure

The primary outcome (H1.1) measure is self-reported number of days of risky (illicit or nonmedical) opioid use in the past 180 days, assessed at 6 months after the baseline visit using single items based on questions used in the Addiction Severity Index (ASI) [3,4], and Current Opioid Misuse Measure (COMM) [5,6]. Participants are asked to specify the number of days of illicit opioid use and of nonmedical opioid use in the past 30 days (range is 0-30 days). Illicit opioid use includes use of heroin or synthetic opioids. Nonmedical opioid use includes using prescribed opioids more than prescribed (e.g., taking 2 tablets when the prescription indicates a dose of 1 tablet) or taking pharmaceutical opioids that were not prescribed to the individual taking them. Prescription opioids may be prescribed by the participating PCP or by another medical provider. The measure is calculated as the sum of all days of use reported on the assessments of past 30-day drug use for the first 6 months (i.e., the sum of days of use from the measures collected on day 30, day 60, day 90, day 120, day 150, and day 180).

7.2 Analysis of the Primary Outcome Measure

7.2.1 Calculation of the Number of Days of Risky Opioid Use for the Primary Outcome

Days of risky opioid use as measured in the Healthy Living Monthly Survey (HLM) will be used for the primary outcome analysis. No other data source, including Timeline Followback (T01), will be incorporated into the primary outcome analysis. The decision rule for generating the number of days of risky opioid use (illicit opioid use and nonmedical opioid use) during the past 30 days is to add up the days of different kinds of risky opioid use (e.g., use own prescription opioid medications more than prescribed, use opioid medications belonging to someone else, etc.), and then subtract the days when the risky opioid use was counted multiple times due to overlap (e.g., using heroin or fentanyl on the same day as using prescription opioids more than prescribed should only count as one day). The days of different kinds of risky opioid use are collected in the following questions:

For patient participants that report they currently have a prescription for an opioid pain medication (HMOPIRX=1):

- a) (HMPNKOTH) During these 30 DAYS, on how many days did you need to take pain medications **belonging to someone else?** (Enter "0" for never);
- b) (HMRXMORE) During these 30 DAYS, on how many days did you have to **take more of your medication than prescribed?** (Enter "0" for never);

For patient participants that do not report currently having a prescription for an opioid pain medication (HMOPIRX=0):

- c) (HMOPINP) During these 30 DAYS, on how many days did you use **prescription opioid medications** that were not prescribed to you? (Enter "0" for never)

For all patient participants:

d) (HMHERFYL) During these 30 DAYS, on how many days did you use **heroin or fentanyl?** (Enter "0" for never)

The days of overlap are collected in the following questions:

For patient participants that report currently having a prescription for an opioid pain medication (HMOPIRX=1) and reported > 0 days for both HMPKOTH and HMRXMORE:

e) (HMPOSDNY) During these 30 DAYS, did you ever use your own prescription opioid medications more than prescribed **on the same day** that you used opioid medications that belonged to someone else? (y/n);

f) If the answer to HMPOSDNY is Yes: (HMPOSDDY) During these 30 DAYS, on how many days did you use your own prescription opioid medications more than prescribed **on the same day** that you used opioid medications that belonged to someone else? (Enter "0" for never)

For all patient participants that reported > 0 days for HMHERFYL **and** > 0 days for (HMPKOTH **or** HMRXMORE **or** HMOPINP):

g) (HMHEROPI) During these 30 DAYS, did you ever use heroin or fentanyl **on the same day** you used prescription opioid medications more than prescribed or that were not prescribed to you (including medications that belonged to someone else)? (y/n)

h) If the answer to HMHEROPI is Yes: (HMHEROOSP) During these 30 DAYS, on how many days did you use heroin or fentanyl **on the same day** you used prescription opioid medications more than prescribed, or that were not prescribed to you (including medications that belonged to someone else)? (Enter "0" for never)

Therefore, the algorithm of generating the days of risky opioid use in the past 30 days to adjust for the days of overlap when different types of risky opioid use occurred on the same day is to:

For patient participants with HMOPIRX=1:

1. Add the items (a) and (b) and subtract (e/f)
2. Add the result from #1 to (d) and subtract (g/h)

For patient participants with HMOPIRX=0:

1. Add the items (c) and (d) and subtract (g/h)

If the calculated days of risky opioid use in the past 30 days is greater than 30 based on the algorithm (e.g., due to the patient participant incorrectly completing the overlap questions), the calculated days of risky opioid use in the past 30 days will be set to 30.

When there are multiple submissions collected for HLM from the same patient participant in the same month, the data from the first submission will be used to calculate the primary outcome. If the data from the first submission is missing, the data in the second submission will be used to calculate the primary outcome. In general, the primary outcome will be calculated from the first collected non-missing data.

The number and percent of patient participants with the primary outcome data collected in the 6 monthly surveys will be summarized by intervention treatment arm. The primary outcome is considered available for a patient participant if all the questions for risky opioid use (illicit and non-medical) are completed on all six of the monthly surveys. Multiple imputation will be used to impute missing primary outcome data so that there are no missing outcome data in the primary outcome analysis.

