7.3 Other Outcome Measures

The following additional measures will be collected to assess exploratory outcomes, characterize domains from our conceptual model, and may be used to adjust models of the primary and secondary outcomes. These measures are collected at the baseline study visit and at the study visits specified in Tables 5 and 6 (schedule of assessments).

- a. Demographic characteristics and insurance status.
- b. Patient participants' self-assessments of readiness to change risky opioid use and other substance use will be measured using two items that query self-reported readiness and confidence to change, rated on a 10-point scale.
- c. Social support will be assessed using the PROMIS instrumental and emotional health short forms.
- d. Patient engagement in primary care (Exploratory Objective 1): Number and frequency of kept appointments and missed appointments for primary care visits.
- e. Addiction treatment and harm reduction program utilization (Exploratory Objective 4): Self-reported number of weeks of addiction treatment or harm reduction program services, and self-reported number of weeks receiving MOUD is assessed at baseline and at 6 and 12 months. Prescriptions for MOUD received in the primary care clinic are additionally assessed from the EHR from at 12 months.
- f. PCP knowledge and attitudes regarding substance use, subthreshold OUD, and opioid management, assessed at baseline and at the end of the intervention period.
- g. TLFB measure of substance use in the past 90 days (Exploratory Objective 5): A 90-day TLFB administered at the 3- and 6-month quarterly assessments, will capture days of risky opioid use, days of binge alcohol use, and other drug use including benzodiazepines, cocaine, stimulants, marijuana, and other drugs. For any prescription opioids, benzodiazepines, and amphetamine-type stimulants, the TLFB will measure non-medical use.
- h. Patient participant-completed assessments will measure PCP counseling on opioid use (Exploratory Objective 6). For patient participants who have a PCP encounter integrated with the baseline research visit, counseling is measured with the baseline exit survey. For all patient participants, information on any discussion or counseling provided during follow-up PCP encounters will be assessed with a quarterly patient experience questionnaire.

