PROMIS instrumental and emotional health short forms	SA			X			X				(-) 1 / (+) 3 weeks
Addiction treatment and harm reduction program utilization	SA			X			X		X		(-) 1 / (+) 3 weeks
Urine Drug Screen	RA			X			X		X		(-) 1 / (+) 3 weeks
Assessment of blinding	RA						X		X		N/A
Study Administration											
Inventory – Supplies Form	RA									X	N/A
Recruitment Log	RA									X	N/A
Missed Visit and Visit Documentation Form	RA			X		X	X	X	X		(-) 1 / (+) 3 weeks
Monthly Survey Link	RA									X	N/A
Progress Note Checklist ⁴	RA									X	N/A
Protocol Deviation	RA									X	N/A
Visit Compensation Log ⁵	RA									X	N/A
RA Recorded ED visits and hospitalizations	RA									X	N/A
Mental Health Follow-Up Assessment	RA									X	N/A
Study Completion Form	RA									X	N/A
Death Form	RA									X	N/A

¹ Assessment completed within the prescreener survey but is considered a baseline assessment if the participant screens eligible and is enrolled into the study.

² Adapted COMM provided to individuals receiving any opioid therapy in the past 6 months.

³ RA – Research Assistant or Research Coordinator Administered; SA – Self Administered++ = Not captured in eClinical

* = Completed as part of pre-screening for study eligibility

** = May be done after the baseline visit, if there is not enough time to complete before.

*** = Survey is only given to patients who have an integrated PCP and baseline visit

Note – TLFB at 3 and 6 months cannot be completed earlier than or on the target visit date.

Note – All participant-facing documents will be reviewed/approved by the IRB. Minor edits may be made to assessments (e.g., grammar, punctuation, directions, system programming, etc.) as needed. Assessments will only be submitted for re-review if information to be collected is changed (e.g., addition of new questions.).

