11.5.3 Timeline Follow-Back (TLFB)

The Timeline Follow-Back procedure (Sobell et al., 1988) will be used to elicit the patient participant's self-reported use of substances (opioids and other drugs, binge alcohol), diet and exercise (≥ 20 min) in the past 90 days.[58] The TLFB will be administered by the RC/RA by phone or in person as part of the 3-month and 6-month assessment battery, to document the patient participant's self-reported use of substances for each day since the previous TLFB assessment.

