14.10 Missing Data and Dropouts

The primary outcome, number of days of risky opioid use within the first 180 days since baseline, is measured by repeated monthly assessments. For each monthly assessment, participants will record the number of days of risky use within the previous 30 days. We consider two types of missing data for this outcome:

- *Missingness due to dropout*: participants may withdraw early from the study and miss all subsequent monthly measurements.
- *Intermittent missingness*: participants may miss one or more monthly surveys while remaining enrolled in the study.

It is anticipated that up to 20% of participants may be missing data for the primary endpoint due to dropout and/or nonresponse. It is possible that participants who drop out will have higher use after their dropout date than those who remain in the study. For example, it is possible that days of use after the withdrawal timepoint for dropouts in the treatment arm may more closely resemble that of controls than that of other treated participants. In this case it is possible that a complete case analysis could overestimate the treatment effect if there is a high level of missing data (and if control dropouts do not have an analogous increase). Multiple imputation will be performed for the primary analysis to account for missingness of the primary outcome variable. A repeated measures model with treatment by time interactions will be created for the imputation in order to take full advantage of information from partial reports by participants with intermittent missingness. Information on days of risky use assessed by TLFB will be included in the imputation model. Further details of the imputation models will be specified in the SAP. If multiple imputation is performed, a complete-case analysis will be performed as a secondary analysis. In either case, sensitivity analyses will be performed to assess robustness of the treatment effect estimate to different patterns of responses for the missing values.

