7.2.3 Multiple Imputation for Missingness of the Primary Outcome

The primary outcome, number of days of risky opioid use within the first 180 days since baseline, is measured by repeated monthly assessments. For each monthly assessment, participants will record the number of days of risky use within the previous 30 days. We consider two types of missing data for this outcome:

- *Missingness due to dropout*: patient participants may withdraw early from the study and miss all subsequent monthly measurements.
- *Intermittent missingness*: patient participants may miss one or more monthly surveys, or fail to complete the opioid items on the survey, while remaining enrolled in the study.

It was anticipated during the study design stage that up to 20% of participants may be missing data for the primary endpoint due to dropout and/or nonresponse. Exclusion of those participants with missing values could lead to underestimation of variance and biased estimated parameters. Multiple imputation (MI) will be performed for the primary analysis to account for missingness of the primary outcome variable. For the sake of best practice, if a patient participant misses the response values at baseline and in each of the monthly surveys for the risky opioid use questions for all 12 post-baseline collections, the patient participant will be excluded from multiple imputation since the analysis has little or no information to inform what those actual values might have been.

Multiple imputation consists of three steps:

1. Imputation step. An 'imputation' generally represents one set of plausible values for missing data – multiple imputation represents multiple sets of plausible values. When using multiple imputation, missing values are filled in to generate multiple completed datasets.
2. Completed-data analysis (estimation) step. The desired analysis is performed separately for each dataset that is generated during the imputation step.
3. Pooling step. The results obtained from each completed data analysis are combined into a single multiple imputation result.

Data for the primary outcome analysis is collected from the HLM survey. The analysis dataset includes monthly risky opioid use in Month 1, Month 2, Month 3, ..., Month 6 for the first 6 months post-enrollment, along with baseline risky opioid use, site, treatment, and PCP cluster.

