15.0 UPDATES TO THE STATISTICAL ANALYSIS PLAN

Table 4: SAP Revision History		
SAP Version	Date of Approval	Summary of Changes
1.0	02JUL2024	Initial Version
2.0	23MAY2025	Added Section 14 ADDENDUM for zero-inflated negative binomial post hoc analyses of the primary outcome

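### The primary imputation omits the timeline follow-back days that the protocol commits to, without explanation, and its code treats any gap running through Month 6 as dropout, including in STOP participants who are still enrolled

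*SAP*

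**What the plan says.** **TLFB.** Protocol 14.10 states: "Information on days of risky use assessed by TLFB will be included in the imputation model". It then leaves the rest to the SAP: "Further details of the imputation models will be specified in the SAP". SAP 7.2.1 states: "No other data source, including Timeline Followback (T01), will be incorporated into the primary outcome analysis". Both PROC MI steps in SAP 7.2.3 list treatment, site, baseline and the six monthly counts, with no TLFB variable. The only change logged in SAP 15.0 after the initial version is "Added Section 14 ADDENDUM for zero-inflated negative binomial post hoc analyses of the primary outcome".

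On what TLFB covers, Protocol 7.3 says: "A 90-day TLFB administered at the 3- and 6-month quarterly assessments, will capture days of risky opioid use". Protocol 11.5.3 says it records "use of substances for each day since the previous TLFB assessment". A note to Protocol Table 6 adds: "TLFB at 3 and 6 months cannot be completed earlier than or on the target visit date".

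**Dropout.** SAP 7.2.3 describes missingness due to dropout thus: "patient participants may withdraw early from the study and miss all subsequent monthly measurements". It calls missingness intermittent when surveys are missed by someone who stays enrolled. Intermittent gaps are assumed missing at random (MAR), on the ground that the intervention effect continues during enrolment. Dropout gaps are assumed not at random and are filled from EUC observations, on the ground that the person has left the study environment. The analysis data set holds baseline and Months 1-6 only. The Table 2 example calls a missing Month 6, or missing Months 5-6, dropout.

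**Exclusion.** SAP 7.2.3 excludes a participant who lacks baseline and all 12 surveys. The footnote to appendix Table 30 excludes one who lacks baseline and all 6.

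**The concern.** The first issue is an unexplained departure from the protocol in the primary analysis. Deferring further details to the SAP does not cover removing a source that the protocol says will be used. TLFB is the only other planned self-report of days of risky use over the same 180 days. It is taken by interview at 3 and 6 months, so it may exist for people who skip the electronic monthly survey. No planned sensitivity analysis uses it.

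The second issue is that the text and the code of SAP 7.2.3 do not describe the same rule. The stated reason for borrowing from EUC does not fit a STOP participant who is still enrolled and answers again later. An analyst who follows the definitions and one who follows the code would treat that participant differently in the primary analysis.

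**Working it through.** **1. TLFB coverage.** Two interviews of 90 days each, at months 3 and 6, cover 2 × 90 = 180 days. The Table 6 note rules out early completion. The two interviews therefore span about the same window as the primary outcome.

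**2. Three STOP participants, none withdrawn, traced through the two steps.** Step 1 runs by arm with `impute=monotone`, so it fills only gaps that are followed by an observed month within Months 1-6. Step 2 fills everything left, using regressions fitted to EUC.

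| Surveys | Under the definitions | Under the code |
|---|---|---|
| Missing 5, answers 6 | MAR within arm | Step 1, within arm |
| Missing 4-6, answers 7-12 | MAR within arm | Step 2, EUC-based |
| Baseline known, missing 1-6, answers 7-12 | MAR within arm | Step 2, all six EUC-based |

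Once a month is missed, the code's split depends only on whether a later month up to Month 6 is observed. Neither step uses withdrawal status or Months 7-12.

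**3. Data generator.** Size was judged with the SAP Section 10 planning model: Scenario 1, 20 against 14 days per 90; PCP variance 0.15; individual variance 0.25; logit scale. It gives PCP-mean quartiles of 17.2 and 25.3 (SAP: 17 and 25). Power for 60 PCPs × 5 patients with 20% dropout is 0.953 with one individual intercept per person and 0.972 with a fresh one per interval (SAP: 0.97). Some other cells match the SAP less closely with a single intercept (for example 0.885 against 0.93 for 50 × 4). Nothing below depends on power.

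**4. Size.** Let *s* be the share of STOP participants who are still enrolled with a gap through Month 6, and *d* the extra days each receives from EUC-based rather than own-arm values. Then

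RR = RR(MAR) + *s* × *d* / EUC mean.

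The generator gives RR(MAR) = 0.7206. The EUC mean is about 43.1 days per 180, because the random intercepts raise it above 40. The share *s* = 5-20% is assumed; 20% is the SAP's ceiling for all missingness. The values of *d* come from large-sample sequential regressions (300,000 per arm). They are shown with earlier months only as predictors, and with baseline added as in the SAP's variable list.

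| Gap | *d*, months only | *d*, with baseline | RR with baseline, *s* = 5% to 20% |
|---|---|---|---|
| 1 month | 0.17 | 0.46 | 0.721 to 0.723 |
| 2 months | 0.42 | 1.1 | 0.722 to 0.726 |
| 3 months | 0.83 | 2.0 | 0.723 to 0.730 |
| 6 months | 12.05 | 12.0 | 0.735 to 0.777 |

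For example, with three months and 20%: 0.7206 + 0.20 × 2.0 / 43.1 = 0.730. As a share of the log rate ratio, 1 − ln(0.730)/ln(0.7206) is about 4%. For all six months missing, the loss is about 6% at *s* = 5% (0.7346) and about 23% at *s* = 20% (0.7765). With assumed extra month-to-month noise (logit SD 1) and months-only predictors, 0.760 becomes 0.761-0.773 for gaps of one to three months and 0.772-0.808 for six.

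**5. TLFB gain.** The documents give no correlation between TLFB and survey days and no completion rate among survey skippers, so no size follows from them.

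**The case against.** On TLFB, the SAP is explicit and its code agrees, so no analyst would be in doubt about what to run. Exclusion may also be sound. Research staff administer TLFB, Protocol 10.10.2 says they cannot be blinded, and Protocol 6.1 and 11.0 prefer self-administration for substance use to limit social desirability bias. That stands as a possible justification, but the SAP does not state it.

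On dropout, the SAP introduces its monotone and non-monotone patterns as features of the primary analysis data set, which stops at Month 6. Read so, the patterns, Table 2, the code and Tables 30-31 agree, and the rule is deterministic. This reading still conflicts with the definitions by enrolment status and with the reason given for the EUC-based step.

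The SAP also calls the step conservative, and SAP 7.3 plans full-MAR and complete-case analyses. Protocol 10.9 lets a missed survey be completed the next month, which should remove some gaps at Month 6 alone. All of this limits the consequence. However, both sensitivity analyses also change how true dropouts are handled, so they do not isolate this rule.

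**Conclusion.** Both conflicts are in the text and should be resolved. They are faults of specification, not evidence of an important bias. For short gaps the shift is small and toward a rate ratio of 1. It is larger only if most or all of Months 1-6 are missing in participants who remain enrolled. These sizes rest on the planning model, a working intervention, and assumed shares and gap lengths; the 0-30 limits were not imposed in the table.

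Three stronger inferences are not supported:

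- A reader might infer that still-enrolled STOP participants will in fact be given EUC-based values and that the primary estimate is materially diluted. The documents do not show that any such participant exists.
- A reader might infer that the TLFB conflict leaves the primary analysis undefined. SAP 7.2.1 settles what will be run; what is missing is the reason for departing from the protocol.
- A reader might infer that the two exclusion rules give importantly different analysis sets. They differ only for someone with no baseline and no Months 1-6 data but a later survey. Baseline survey days are collected at prescreening, so few if any participants should be affected.

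**What to change.** - **Flag.** Define dropout once, with a participant-level flag: for example, withdrawal status and date from the Study Completion form, or no monthly survey after the last observed one through Month 12.
- **Step 1.** Impute all gaps within arm under MAR, with Months 7-12 and the 3- and 6-month TLFB days as auxiliary variables.
- **Step 2.** Reset flagged dropouts' post-dropout months to missing, along with any TLFB values that were imputed rather than observed. Apply the EUC-based step to those participants only. Do not rely on variable order with `impute=monotone` to separate them: an observed 6-month TLFB placed after the months it covers would turn a true dropout's gap into an interior one, filled within arm.
- **TLFB.** Limit the SAP 7.2.1 sentence to calculation of the observed outcome. If the omission is deliberate, state and justify the departure from Protocol 14.10 and report an imputation with TLFB as a sensitivity analysis.
- **Tidy.** Align Table 2 and Tables 30-31 with the flag and use one exclusion rule. Correct the SAP 7.2.3 sentence implying that every variable of the Section 7.2.2 model enters the imputation, since PCP cluster does not.

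The cost is SAP wording, a derived flag, table footnotes and some lines of code. All the data are already scheduled for collection. If the primary analysis has been run, record the rule used and report the alternative as a sensitivity analysis.
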